#### 8.2.1.2. Adverse Event Severity

The Investigator will assess the grade of the AE according to the NCI CTCAE, Version 4.03 or higher.

Toxicities that are not specified in the NCI CTCAE, Version 4.03 or higher, will be defined as follows:

- Grade 1: Mild; asymptomatic or mild symptoms; clinical or diagnostic observations only; intervention not indicated
- Grade 2: Moderate; minimal, local, or noninvasive intervention indicated; limiting age-appropriate instrumental activities of daily living (ADL)
- Grade 3: Severe or medically significant but not immediately life-threatening; hospitalization or prolongation of hospitalization indicated; disabling; limiting self-care ADL
- Grade 4: Life-threatening consequences; urgent intervention indicated
- Grade 5: Death related to AE

Note: it is important to distinguish between SAEs and severe AEs. Severity is a measure of intensity, whereas seriousness is classified by the criteria based on the regulatory definitions as described in [Section 8.1.2](#).

#### 8.2.1.3. Abnormal Laboratory Values

The Investigator is responsible for reviewing laboratory test results and determining whether an abnormal value in a subject represents a clinically significant change from the subject's baseline value. In general, abnormal laboratory findings without clinical significance (based on the Investigator's judgment) should not be recorded as AEs. In general, abnormal laboratory test results should be reported as an AE if the laboratory result:

- requires an adjustment or discontinuation of duvelisib
- requires treatment or adjustment to current therapy
- is considered to be an AE by the Investigator

#### 8.2.1.4. Medication Errors, Misuse and Abuse of Study Drug

Overdose, medication error, misuse, and abuse are defined as follows:

- Overdose: refers to the administration of a quantity of study drug given per administration or cumulative, which is above the maximum dosage according to the protocol. Clinical judgment should always be applied

- Medication error: refers to an unintentional error in dispensing or administration of study drug not in accordance with the protocol
- Off-label use: relates to situations where the study drug is intentionally used for a medical purpose not in accordance with the protocol
- Misuse: refers to situations where the study drug is intentionally and inappropriately used not in accordance with the protocol
- Abuse: corresponds to the persistent or sporadic intentional excessive use of the study drug, which is accompanied by harmful physical or psychological effects
- Occupational exposure: refers to the exposure to the study drug as a result of one's professional or nonprofessional occupation
- Overdoses, medication errors, misuse, or abuse will be collected as part of investigational medicinal product dosing information and/or as a protocol violation, as required.

Any AE associated with an overdose, medication error, misuse, or abuse of duvelisib should be recorded on the AE eCRF with the diagnosis of the AE.

#### 8.2.2. Reporting of Serious Adverse Events

A SAE Report Form will be completed and submitted to the Sponsor or designee within 24 hours of the Investigator's first knowledge of the event, even if the experience does not appear to be related to duvelisib, from the time the subject signs the ICF through 30 days after the last dose of duvelisib. Please refer to the SAE Report Form for where and how to submit the form.

The initial SAE report form must be as complete as possible, including details of the current illness and (serious) AE, and an assessment of the relationship between the event and duvelisib. Additional information relating to a previously reported SAE must also be reported within 24 hours of the Investigator's first knowledge of information. The Investigator may also be asked, by the Sponsor, to provide clarifications or additional information. If the Investigator becomes aware of an SAE, considered related to duvelisib by the Investigator, occurring more than 30 days after the last dose of duvelisib, the SAE must be reported as described above.

##### 8.2.2.1. Immediate Reporting of Medical Events of Interest

The following are medical events of interest (MEOIs) and, therefore, must be reported to the Sponsor or designee on a SAE/MEOI report form within 24 hours of the Investigator's knowledge of the MEOI, whether serious or not and regardless of relationship to duvelisib:

- Reports or laboratory results of AST or ALT  $> 3 \times$  the upper limit of normal (ULN) in combination with bilirubin  $> 2 \times$  ULN.
- Clinical findings of Grade 3 or higher rash. Preexisting skin conditions that recur would not meet this definition unless the recurrence is of a greater severity or frequency than previously experienced.

### 8.2.2.2. Reporting of Serious Adverse Events to Regulatory Authorities, Ethics Committees and Institutional Review Boards

The Sponsor will determine the expectedness of each reported SAE based on the appropriate reference safety information for the Verastem product, in accordance with local requirements. The Sponsor or designee shall notify regulatory authorities of serious, unexpected, and related AEs or other AEs, according to local requirements. Serious, unexpected, and related AEs reported for subjects receiving a non-Verastem study drug will be also submitted according to local requirements.

The Sponsor or designee shall notify the Investigator of serious, related, and unexpected AEs submitted to the regulatory agencies, according to local country requirements.

The Sponsor or designee shall notify the appropriate Central Ethics Committees (CEC), Institutional Review Boards (IRBs), and Local Ethics Committees (LECs) of serious, related, and unexpected AEs or significant risks to subjects, in accordance with local country requirements.

The Investigator must keep copies of all AE information on file, including correspondence with the Sponsor and CECs/IRBs, and LECs.

### 8.2.3. Pregnancy and In Utero Drug Exposure

Since duvelisib has not been evaluated in pregnant or nursing women, the treatment of pregnant women or WCBP who are not using effective contraception is contraindicated (see [Section 6.6.11](#) and [Section 6.2.4](#) for instructions on birth control and pregnancy testing, respectively).

Pregnancies occurring in female subjects or partners of male subjects are considered immediately reportable events if the pregnancy occurs during the study treatment through 30 days after the subject's last dose of duvelisib. If a pregnancy occurs in a subject, duvelisib must be discontinued immediately. The pregnant woman should be referred to an obstetrician/gynecologist experienced in reproductive toxicity for further evaluation and counseling.

The pregnancy must be reported to the Sponsor or designee within 24 hours of the Investigator's knowledge of the pregnancy using the Pregnancy Notification Form.

The Investigator will follow the pregnant subject until completion of the pregnancy and must notify the Sponsor of the pregnancy outcome within 24 hours of the Investigator's knowledge of the outcome. The Investigator will provide this information on the Pregnancy Outcome Report Form. This notification includes pregnancies resulting in live, "normal" births.

If the pregnant subject experiences an SAE during pregnancy, or the outcome of the pregnancy meets any of the serious criteria (ie, spontaneous abortion [any congenital anomaly detected in an aborted fetus is to be documented], stillbirth, neonatal death, or congenital anomaly), the Investigator should follow the procedures for reporting SAEs (ie, reporting the event to the Sponsor or designee within 24 hours of the Investigator's knowledge of the event).

All neonatal deaths and congenital anomalies that occur within 30 days of birth (regardless of causality) should be reported as SAEs to the Sponsor or designee. In addition, any infant death or congenital anomaly occurring after 30 days that the Investigator suspects is related to the in utero exposure to duvelisib should also be reported to the Sponsor or designee.

## 9. STATISTICAL METHODS

Details of the statistical methods for this study will be documented in a Statistical Analysis Plan (SAP). The SAP may modify the statistical methods outlined in the protocol; however, any major modification will also be reflected in a protocol amendment.

### 9.1. Sample Size

The study population will consist of subjects who received duvelisib or participated in the survival follow-up phase in a previous duvelisib study.

The number of subjects will be based on the number of eligible subjects in previous duvelisib studies approved for this long-term continued treatment and follow-up study.

### 9.2. Analysis Sets

One analysis set is defined in this section, with any additional analysis sets to be defined in the SAP.

#### 9.2.1. All-Treated Analysis Set

The All-treated Analysis Set (ATS) will include all subjects who receive any amount of duvelisib on or after C1D1 of this study. The ATS will be the primary analysis set for all safety endpoints.

### 9.3. Efficacy Analyses

Analyses of efficacy endpoints may be performed, as appropriate, according to the SAP of the subject's previous study. No analyses of efficacy endpoints are planned for this study.

### 9.4. Safety Analyses

Adverse events will be coded by using the Medical Dictionary for Regulatory Activities (MedDRA) version 16.1 or higher and will be graded according to the CTCAE, version 4.03 or higher.

Summaries of AEs will be focused on treatment-emergent AEs (TEAEs). In this long-term extension study, a TEAE is defined as any AE with an onset date on or after C1D1 and within 30 days after the last dose of duvelisib. TEAEs will be summarized by MedDRA system organ class and preferred term. Separate summaries for TEAEs related to duvelisib, TEAEs that led to treatment discontinuation, TEAEs that led to death, TEAEs by CTCAE grade, TEAEs of Grade 3 or higher, serious TEAEs, and serious TEAEs related to duvelisib will be provided.

Baseline laboratory values will be those collected at C1D1 of this long-term extension study, or if not available, the most recent values collected within 30 days before C1D1. Applicable laboratory values will be graded according to CTCAE criteria. Shifts from baseline to maximum postbaseline grades will be tabulated for hematology, blood chemistry, and LFTs.

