| Duvelisib administration                            | ---                        | ---                                     | X                                       |   |                                    |
| Survival  |                            |   | X                                       |   | X                                  |

*Table footnotes appear on the following page.*

Abbreviations: AE = adverse event;  $\beta$ -hCG =  $\beta$  human chorionic gonadotropin; C1D1 = Cycle 1 Day 1; CR = complete response; ICF = informed consent form; MR = minor response; PE = physical examination; PR = partial response; SAE = serious adverse event; SD = stable disease; TT = Treatment Termination; WCBP = women of childbearing potential.

a Procedures captured on the previous duvelisib study within 30 days of C1D1 do not need to be repeated, unless otherwise specified. bException: Radiologic evaluations and response assessments performed on the previous duvelisib study within 60 days of C1D1 do not need to be repeated at the C1D1 visit.

b The TT Visit should be scheduled no more than 7 days after the decision to terminate duvelisib. Assessments performed within the previous 2 weeks, or previous 30 days for investigator response assessments, need not be repeated at the TT visit.

c All subjects will have a Safety Follow-up visit approximately 30 (+ 7) days after the last dose of duvelisib. At a minimum, this visit should include collection of AEs/SAEs and concomitant medications/procedures. This visit can be performed by telephone call as long as the subject does not require laboratory and/or other procedures related to any new or ongoing AEs, in which case a clinic visit will be required.

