### 4.3. Treatment Discontinuation

Treatment discontinuation occurs when a subject is no longer receiving any duvelisib. A subject should be discontinued from duvelisib if, in the opinion of the Investigator, it is medically necessary, or if it is the wish of the subject.

Subjects will be discontinued from treatment in case of any of the following reasons:

- An AE or unacceptable toxicity that requires discontinuation of duvelisib
- Disease progression
- Subject death
- Noncompliance to protocol
- Investigator decision
- Subject becomes pregnant
- Subject lost to follow-up
- Termination of the study by the Sponsor
- Voluntary withdrawal from study treatment by subject

Adverse events leading to the discontinuation of a subject will be followed until the event resolves, resolves to baseline, or is considered stable or chronic.

If a subject discontinues duvelisib, then a Treatment Termination (TT) Visit should occur within 7 days after the last dose of duvelisib. Each TT assessment need not be performed if the subject has had all the same assessments within the previous 2 weeks.

All subjects receiving duvelisib will have a Safety Follow-up visit approximately 30 (+ 7) days after the last dose of duvelisib. If possible, this visit should occur before the initiation of any subsequent anticancer therapy. At a minimum, this visit should include collection of AEs/serious AEs (SAEs), and concomitant medications/procedures. This follow-up visit may be performed by telephone call as long as the subject does not require laboratory and/or other procedures related to any new or ongoing AEs, in which case a clinic visit will be required.

Subjects who discontinue duvelisib and have not withdrawn consent from overall study participation will enter the survival follow-up period described in [Section 6.5](#).

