### 6.5. Survival Follow-up Assessments for All Subjects

Subjects receiving duvelisib treatment will be followed for OS after discontinuation of duvelisib as indicated in [Table 1](#). Subjects enrolled only in the survival follow-up portion of this study will be assessed according to [Table 2](#).

All subjects will be followed for OS for the duration of time outlined in their previous duvelisib study. Survival follow-up will occur every 6 months ( $\pm$  4 weeks). Information on initiation of

other anticancer therapy will also be collected and should include therapy name(s), start and stop date(s) of other subsequent therapies, as well as the best response on the subsequent therapies, as applicable. This assessment can be conducted by telephone interview.

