6.7 Unscheduled Visits

Unscheduled visits will not be included in by-visit summary tables, unless otherwise specified. For laboratory tests, data from unscheduled visits will be included in listings and summaries of maximum changes from baseline, and the best or worst post-baseline values.

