7.3 Safety Analyses

7.3.1 Adverse Events

Adverse events will be coded using MedDRA Version 19. The Grade of the AE will be assessed according to the NCI-CTCAE Version 4.03. If an AE is not included in the NCI-CTCAE Version 4.03, the Grade of the AE will be assessed according to the protocol, Section 8.2.1.2.

The summary of AEs will be focused on treatment-emergent AEs. Since this is an extension study, a treatment-emergent AE (TEAE) is defined as any AE that is reported out to 30 days after the last dose of study treatment. The onset date of an AE will be compared to the last dose date plus 30 days to determine whether the AE is treatment-emergent or not.

TEAEs will be summarized for each treatment arm by MedDRA system organ class (SOC) and preferred term (PT), or PT only. For summary tables by SOC and PT, SOC will be sorted alphabetically and PT will be sorted by decreasing frequency in the duvelisib arm within each SOC. For summary tables by PT only, PT will be sorted by decreasing frequency in the duvelisib arm.

If multiple TEAEs of the same PT occur within a subject, only the maximum grade observed for this PT will be used in summary of TEAEs by grade, the subject will be counted only once in the number of subjects for this PT and only once for the number of subjects for the SOC to which this PT belongs.

An overview TEAE summary table will be provided, which will include the number of subjects with AEs in selected categories. In addition, TEAEs will be summarized for the following categories, and will be tabulated by SOC and PT, unless otherwise specified.

- Treatment-emergent AEs
- Treatment-emergent AEs related to duvelisib
- Treatment-emergent AEs leading to treatment discontinuation
- Treatment-emergent AEs by maximum grade
- Grade 3 or higher treatment-emergent AEs
- Treatment-emergent SAE
- Treatment-emergent SAE related to duvelisib

Adverse events of special interest (AESI) will be summarized overall and with grading specifications. The AESI categories and associated PT's are provided in Appendix A of this document.

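### Neither the TEAE window nor the worst-grade laboratory summaries take account of the start of subsequent anticancer therapy, so findings that arise under the next regimen can enter the primary safety tables

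*Protocol*

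**What the plan says.** Adverse events and safety laboratory values are the primary endpoints (Protocol 3.1, SAP 5.1).

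- **Adverse events.** Protocol 9.4 counts "any AE with an onset date on or after C1D1 and within 30 days after the last dose of duvelisib". SAP 7.3.1 applies the same upper limit: "The onset date of an AE will be compared to the last dose date plus 30 days". Neither section mentions subsequent anticancer therapy.
- **Laboratory values.** Protocol 9.4 states: "Shifts from baseline to maximum postbaseline grades will be tabulated for hematology, blood chemistry, and LFTs". SAP 6.7 says that "data from unscheduled visits will be included in listings and summaries of maximum changes from baseline, and the best or worst post-baseline values". SAP 7.3.2, the laboratory section, gives no last date for a post-baseline value.
- **Follow-up visit.** Table 1 of the protocol, footnote c: "All subjects will have a Safety Follow-up visit approximately 30 (+ 7) days after the last dose of duvelisib". Protocol 4.3 adds a preference: "If possible, this visit should occur before the initiation of any subsequent anticancer therapy".
- **Next therapy.** Protocol 6.6.5 prohibits other anticancer treatment for subjects who are receiving duvelisib. After that, Protocol 6.5 asks that the information collected "should include therapy name(s), start and stop date(s) of other subsequent therapies".

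**The concern.** Disease progression is a listed reason to stop duvelisib (Protocol 4.3), and a subject who has progressed may start another regimen within the following 30 days. The wording of Protocol 4.3 shows that the authors expected this. From that day on, a new cytopenia, infection or transaminase rise may come from the new regimen, from the disease, or from a late effect of duvelisib. The planned all-causality tables put all three together.

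The study has one treatment, no comparator and no inferential analysis (SAP 3.5), so these descriptive tables are its main result. SAP Appendix A makes every preferred term in the infections class an event of special interest, and it adds neutropenia and transaminase elevation. A new antineoplastic regimen could plausibly cause any of these. A reader of the tables could not tell which events began after the switch.

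**Working it through.** The documents give no sample size, expected rate or other figure on this point, so there is nothing to reproduce. The check is mainly a reading of the rules side by side.

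**1. Can the next regimen fall inside the window?** Yes. The prohibition in Protocol 6.6.5 covers subjects receiving duvelisib, while the TEAE window continues for 30 days after the last dose. The request in Protocol 4.3 concerns when the visit takes place. It does not shorten the analysis window.

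**2. How long can the overlap be for adverse events?** If the next therapy starts s days after the last dose, the overlap is 30 − s days. The values of s below are illustrative.

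| s (days) | overlap (days) |
|---|---|
| 7 | 30 − 7 = 23 |
| 14 | 30 − 14 = 16 |
| 21 | 30 − 21 = 9 |

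The 30-day tail as a share of a subject's whole TEAE window is 30/(T + 30), with T the days on treatment in this study (T assumed).

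| T (days) | tail share |
|---|---|
| 84 | 30/114 = 26.3% |
| 168 | 30/198 = 15.2% |
| 365 | 30/395 = 7.6% |
| 730 | 30/760 = 3.9% |

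These are shares of days, not of events.

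**3. Which tables separate attribution?** Protocol 9.4 and SAP 7.3.1 plan related-only versions for all TEAEs and for serious TEAEs. The Grade 3 or higher, maximum-grade and special-interest tables have none. Laboratory shifts carry no causality attribute.

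**4. When do late laboratory values arise?** The Treatment Termination visit is due within 7 days of the last dose (Protocol 4.3) or of the decision to stop (Protocol 6.3). The safety visit may be a telephone call unless an adverse event calls for laboratory or other procedures (Protocol 6.4). Adverse events are followed until they resolve, return to baseline or become stable or chronic (Protocol 8.2.1). Values after the termination visit therefore come mainly from subjects with an event under follow-up. A sample at the safety visit may be drawn as late as day 30 + 7 = 37. That is outside the TEAE window, yet it can still set the worst grade. This reasoning does not depend on the laboratory marks in the later columns of Table 1.

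**5. How does the size depend on unknowns?** Let p0 be the incidence of an event without the next therapy, f the share of subjects who start it inside the window, and r the risk it adds before the window closes, taken as independent of the earlier history. The added incidence is (1 − p0) × f × r. With f and r each assumed to lie between 10% and 50%:

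- p0 = 30%: from 0.7 × 0.1 × 0.1 = 0.7 to 0.7 × 0.5 × 0.5 = 17.5 percentage points.
- p0 = 60%: from 0.4 × 0.1 × 0.1 = 0.4 to 0.4 × 0.5 × 0.5 = 10.0 percentage points.

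All three inputs are assumptions. The width of the range shows that the documents do not fix the size. For laboratory shifts no bound can be given, because no end of window is stated.

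**The case against.** The best defence is that treatment-emergent is a statement about time, not cause. Last dose plus 30 days matches the collection period for adverse events (Protocol 8.2.1), errs toward inclusion, and is a sound primary rule. Attribution has its own tables, and Protocol 8.2.1.1 tells the investigator to consider alternative causes, of which a new regimen is one. Clinically significant laboratory abnormalities are also reported as adverse events (Protocol 6.2.4 and 8.2.1.3) and so receive a causality assessment. Many subjects will have no laboratory value after the termination visit. The table of events leading to discontinuation is hardly affected, because duvelisib has already stopped.

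All of this stands, and it is why the 30-day window should stay. It does not supply a split for the Grade 3 or higher, special-interest or laboratory shift tables, and it does not give the laboratory window an end.

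Two stronger readings are tempting. A reader might infer that the toxicity of the next regimen is being reported as duvelisib toxicity. The documents show only that it can be counted. Symptoms of progression are recorded as adverse events (Protocol 8.2.1), so part of what occurs after the switch is background. SAP 7.3.1 counts a subject once per preferred term, so a repeat of an earlier event at no higher grade adds nothing. A reader might also infer that a subject who starts new therapy before day 30 makes the visit schedule impossible to meet. The schedule says approximately, and the request to precede new therapy applies only where possible, so nothing is breached.

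**Conclusion.** The gap is real and modest. Adverse events and laboratory grades that arise after the start of subsequent therapy can enter the all-causality tables for both primary endpoints, and the planned output does not identify them. On the adverse-event side the exposure is limited to 30 days after the last dose, to subjects who switch in that time, and to tables without a related-only version. On the laboratory side the rule is open-ended, but the late values it can admit come mainly from visits prompted by adverse events.

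The documents do not support any particular number of affected subjects, and the ranges shown above are illustrations. Nor do they support calling the 30-day rule an error. The conclusion rests on the definitions alone and on the premise, which Protocol 4.3 itself allows for, that some subjects start another therapy before the safety visit.

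**What to change.** - **SAP 7.3.1.** Keep the last dose plus 30 days tables as primary. Flag TEAEs with onset on or after the start of subsequent anticancer therapy, and repeat the overview, Grade 3 or higher, serious and special-interest tables without them as a supplementary summary.
- **Protocol 9.4, SAP 6.7 and 7.3.2.** End the post-baseline laboratory window at the earlier of two dates: the safety follow-up cut-off and the day before new therapy. State whether that cut-off is last dose plus 30 days or includes the further 7 days of the visit window. List later values separately.
- **SAP 6.2.** Add a rule for partial therapy start dates, since the only date rule now covers adverse event onset (SAP 6.2.1). One option is to take the earliest date after the last dose that fits the known parts. The supplementary tables would then exclude the most events, while the primary tables include them all.

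The start dates are already collected, so no visit or treatment rule changes. The cost is some extra programming and one more date convention. A delayed duvelisib effect that appears after new therapy starts would leave the supplementary adverse-event tables and the laboratory shift table. Within the 30 days it would stay visible in the primary adverse-event tables, and any laboratory value would stay in the listing.
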